4.0 Test Schedule

Cycle = 28 days

Tests and procedures	Active Monitoring Phase						
	≤14 days prior to registration	Cycle 1 Day 1 (± 2 days) prior to treatment	Cycle 1 Days 8, 15, 22 prior to treatment	Cycle 2 and beyond Day 1 (± 2 days) prior to treatment	Q 8 weeks from Cycle 1 Day 1 (± 5 days)	Every 3 Cycles starting at end of Cycle 3 (± 5 days)	End of treatment
History and exam, wt, ECOG	X			X			X
Height, Child Pugh score	X						
Vitals ³	X	X	X	X			X
Hematology group WBC, ANC, Hgb, PLT	X	X	X	X			X
Chemistry group Sodium, potassium, chloride, bicarbonate, total protein, albumin, calcium, glucose, BUN, total bilirubin, creatinine, alkaline phosphatase, SGOT (AST), SGPT (ALT)	X	X		X			X
Amylase ^R	X	X	X	X			
Lipase ^R	X	X	X	X			
CA19-9		X		X ⁵			
EKG ^R	X					X	
Echocardiogram	X			X ¹⁰			
Tumor measurement and Imaging (CT or MRI as clinically)	X ¹				X ²		

indicated)							
Pregnancy test	X ⁴						
Patient questionnaire booklet	X ⁹			X ⁹			
Adverse event assessment	X		X	X			
Research Archival Tissue (optional)	X ⁸						
Research Tissue Biopsy (optional)				X ^{7,R}			X ⁶
Research blood samples (Optional)	X			X			X

1. Imaging studies such as CT scans, and MRIs can be performed ≤ 28 days prior to registration. Use same imaging throughout the study. Assessment by physical exam should be done ≤ 14 days prior to registration.
 2. Tumor assessment must be performed at least every 8 weeks. Tumor assessment should be performed at any time during the treatment cycle that disease progression is clinically suspected so that patient can go off treatment and receive other therapy.
 3. Includes weight, blood pressure, pulse and temperature
 4. Women of childbearing potential only. Must be done ≤ 7 days prior to registration.
 5. Only to be collected if $> \text{ULN}$ on Cycle 1 Day 1
 6. If patient has experienced disease progression and at such time a standard of care biopsy is ordered by the treating physician, waste specimen will be collected, fresh frozen and stored for future correlative studies. Perform only if archival specimen was available.
 7. Perform only if archival specimen was available.
 8. Archival FFPE and/or fresh frozen tissue collected in setting of standard of care procedures.
 9. Patient questionnaire booklet must be used; copies are not acceptable for this submission. Booklet should be completed by patient prior to review of treatment response and discussions of patient's general health since last treatment evaluation.

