8.0 Dosage Modification Based on Adverse Events

If multiple adverse events are seen, administer dose based on greatest reduction required for any single adverse event observed. Reductions or increases apply to treatment given in the preceding cycle and are based on adverse events observed since the prior dose.

ALERT: *ADR reporting may be required for some adverse events (See Section 10)*

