8.1 Dose Levels (Based on Adverse Events in Tables 8.2)

Dose Level	Ponatinib
0*	45mg PO once daily
-1	30mg PO once daily
-2	15mg PO once daily

*Dose level 0 refers to the starting dose.

8.2

→ → *Use the NCI Common Terminology Criteria for Adverse Events (CTCAE) version 4.0* unless otherwise specified* ← ←

CTCAE System/Organ/Class (SOC)	ADVERSE EVENT	AGENT	ACTION**
BASED ON INTERVAL ADVERSE EVENT			
Investigations	Neutrophil count decreased ≥ Grade 3	Ponatinib	Omit ponatinib Resume at 45 mg after recovery to ≤ grade 1 Recurrence at 45 mg: Omit ponatinib Resume at 30 mg after recovery to ≤ grade 1 Recurrence at 30 mg: Omit ponatinib Resume at 15 mg after recovery to ≤ grade 1 Recurrence at 15 mg: Discontinue ponatinib

→ → Use the NCI Common Terminology Criteria for Adverse Events (CTCAE) version 4.0* unless otherwise specified ← ←			
CTCAE System/Organ/Class (SOC)	ADVERSE EVENT	AGENT	ACTION**
	Platelet count decreased \geq Grade 3		
Omit ponatinib Resume at 45 mg after recovery to \leq grade 1
 
Recurrence at 45 mg: Omit ponatinib Resume at 30 mg after recovery to \leq grade 1
 
Recurrence at 30 mg: Omit ponatinib Resume at 15 mg after recovery to \leq grade 1
 
Recurrence at 15 mg: Discontinue ponatinib

	Serum amylase increased \geq Grade 3 with no radiographic findings	Ponatinib	
Omit ponatinib Resume at 45 mg after recovery to \leq grade 1
 
Recurrence at 45 mg: Omit ponatinib Resume at 30 mg after recovery to \leq grade 1
 
Recurrence at 30 mg: Omit ponatinib Resume at 15 mg after recovery to \leq grade 1
 
Recurrence at 15 mg: Discontinue ponatinib

	Serum amylase increased \geq Grade 3 with radiographic findings or Grade 4	Ponatinib	
Omit ponatinib Repeat imaging according to clinical care After resolution by imaging, resume at 30 mg after recovery to \leq grade 1
 
Recurrence at 30 mg: Repeat above Resume at 15 mg after recovery to \leq grade 1
 
Recurrence at 15 mg: Discontinue ponatinib

→ → Use the NCI Common Terminology Criteria for Adverse Events (CTCAE) version 4.0* unless otherwise specified ← ←			
CTCAE System/Organ/Class (SOC)	ADVERSE EVENT	AGENT	ACTION**
	Alanine aminotransferase increased (ALT) and/or Aspartate aminotransferase increased (AST) ≥ Grade 3	Ponatinib	Omit ponatinib Resume at 30 mg after recovery to ≤ grade 1 Recurrence at 30 mg: Omit ponatinib Resume at 15 mg after recovery to ≤ grade 1 Recurrence at 15 mg: Discontinue ponatinib

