	Alanine aminotransferase increased (ALT) OR Aspartate aminotransferase increased (AST) ≥ Grade 3 AND Blood bilirubin increased ≥ 2 x ULN AND Alkaline phosphatase > 2 x ULN	Ponatinib	Discontinue ponatinib
Gastrointestinal Disorders	Pancreatitis ≥ Grade 2	Ponatinib	Omit ponatinib Perform ultrasound or abdominal CT scan with contrast If imaging is positive, continue to omit ponatinib and repeat according to clinical care If imaging is negative, or after resolution by imaging, resume at 45 mg after recovery to ≤ grade 1 Recurrence at 45 mg: Repeat above, except resume at 30 mg after recovery to ≤ grade 1 Recurrence at 30 mg: Repeat above, except resume at 15 mg after recovery to ≤ grade 1 Recurrence at 15 mg: Discontinue ponatinib

→ → Use the NCI Common Terminology Criteria for Adverse Events (CTCAE) version 4.0* unless otherwise specified ← ←			
CTCAE System/Organ/Class (SOC)	ADVERSE EVENT	AGENT	ACTION**
	Pancreatitis ≥ Grade 3	Ponatinib	Omit ponatinib Perform ultrasound or abdominal CT scan with contrast If imaging is positive, continue to omit ponatinib and repeat according to clinical care If imaging is negative, or after resolution by imaging, resume at 30 mg after recovery to ≤ grade 1 Recurrence at 30 mg: Repeat above, except resume at 15 mg after recovery to ≤ grade 1 Recurrence at 15 mg: Discontinue ponatinib
	Pancreatitis ≥ Grade 4	Ponatinib	Discontinue ponatinib
Nervous System Disorders	Stroke any Grade	Ponatinib	Discontinue ponatinib
	Peripheral sensory neuropathy ≥ Grade 2	Ponatinib	Please see section 8.43 below for guidance
Cardiac Disorders	Left ventricular systolic dysfunction ≥ Grade 3	Ponatinib	Omit ponatinib Resume at 45 mg after recovery to ≤ grade 1 Recurrence at 45 mg : Omit ponatinib Resume at 30 mg after recovery to ≤ grade 1 Recurrence at 30 mg: Omit ponatinib Resume at 15 mg after recovery to ≤ grade 1 Recurrence at 15 mg: Discontinue ponatinib
	Left ventricular systolic dysfunction ≥ Grade 4		Discontinue ponatinib
	Myocardial Infarction any Grade		Discontinue ponatinib

→ → Use the NCI Common Terminology Criteria for Adverse Events (CTCAE) version 4.0* unless otherwise specified ← ←

CTCAE System/Organ/Class (SOC)	ADVERSE EVENT	AGENT	ACTION**

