Other Non-Hematologic events	≥ Grade 3	Ponatinib	Omit drug and follow patient at least weekly until adverse event has resolved to grade ≤ 2, restart agent at next lower dose level. See sections 8.41 through 8.47 for guidance on other non-hematologic events

* Located at http://ctep.cancer.gov/protocolDevelopment/electronic_applications.ctc.htm

** Use the following to describe actions in the Action column:

- Omit = Treatment is not given for the day/days that are omitted and will not be made up, but treatment may resume once the adverse event has resolved as mandated in Table 8.2. For example, if treatment is omitted on Day 8, but the adverse event has resolved by Day 15, treatment may resume on Day 15.
- Hold/Delay = Treatment can be made up as part of this cycle
- Discontinue = Treatment is totally stopped

NOTE: If the patient experiences a significant adverse event requiring a dose reduction at the start of the next cycle, then the dose will remain lowered for that entire subsequent cycle. If that cycle is completed with no further adverse events >Grade 2, then the dose may be increased, at the investigator's discretion, one level at a time, in the following cycles.

NOTE: Adverse events requiring a dose-reduction step for any or all drugs beyond the two dose-reduction steps (levels -1 and -2) will be at the discretion of the treating physician, if the decision is made for the patient to be kept on study. These dose reductions must be clearly recorded in reported clinical data.

- 8.3 A new course of treatment may begin on the scheduled Day 1 of a new cycle if:
- The ANC is $\geq 1500/\mu\text{L}$;
 - The platelet count is $\geq 75,000/\mu\text{L}$;
 - Any other Ponatinib related adverse event that may have occurred has resolved to \leq Grade 1 or baseline severity.

If these conditions are not met on scheduled Day 1 of a new cycle, the subject will be evaluated at least weekly and the new cycle of treatment will not be initiated until the adverse event has resolved as described above.

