When therapy is resumed it will be considered day one of this new cycle. If Ponatinib was halted during the previous cycle and was restarted with a one-level dose reduction without requiring an interruption for the remainder of the cycle, then that reduced dose level will be initiated on Day 1 of the new cycle. **If ponatinib was omitted for the remainder of the previous cycle or if the new cycle is delayed due to adverse event newly encountered on the scheduled Day 1**, then the scheduled cycle will be started with a one-level dose reduction. If the study drug cannot be restarted within 28 days of the

scheduled Day 1 of a given cycle, the patient will be removed from study treatment and will proceed to event monitoring.

8.4 Additional adverse event guidance:

8.41 Hepatotoxicity: Iclusig can cause hepatotoxicity, including liver failure and death. Fulminant hepatic failure leading to death occurred in an Iclusig-treated patient within one week of starting Iclusig. Two additional fatal cases of acute liver failure also occurred. The fatal cases occurred in patients with blast phase CML (BP-CML) or Philadelphia chromosome positive acute lymphoblastic leukemia (Ph+ ALL). Severe hepatotoxicity occurred in all disease cohorts. Iclusig treatment may result in elevation in ALT, AST, or both. Monitor liver function tests at baseline, then at least monthly or as clinically indicated. Interrupt, reduce, or discontinue Iclusig as clinically indicated.

8.42 Pancreatitis: Clinical pancreatitis occurred in 6% (28/449) of patients (5%, grade 3) treated with Iclusig. Pancreatitis resulted in discontinuation or treatment interruption in 6% of patients (25/449). The incidence of treatment-emergent lipase elevation was 41%. Check serum lipase every 2 weeks for the first 2 months and then monthly thereafter or as clinically indicated. Consider additional serum lipase monitoring in patients with a history of pancreatitis or alcohol abuse. Dose interruption or reduction may be required. In cases where lipase elevations are accompanied by abdominal symptoms, interrupt treatment with Iclusig and evaluate patients for pancreatitis. Do not consider restarting Iclusig until patients have complete resolution of symptoms and lipase levels are less than 1.5 x ULN.

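### Table 8.2 makes the first-occurrence stop for severe ALT/AST elevation with raised bilirubin depend on alkaline phosphatase above 2 x ULN, without saying why

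*Combined protocol and SAP*

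**What the plan says.** Table 8.2 has two rows for transaminases.

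- **Plain row.** The trigger is "Alanine aminotransferase increased (ALT) and/or Aspartate aminotransferase increased (AST") at Grade 3 or above. Ponatinib is omitted and resumed at 30 mg after recovery to Grade 1 or below. After a recurrence it is resumed at 15 mg, and it is discontinued only on recurrence at 15 mg.
- **Combined row.** ALT or AST must be at Grade 3 or above, joined by AND to "Blood bilirubin increased ≥ 2 x ULN AND Alkaline phosphatase > 2 x ULN". The action is to discontinue, which the table notes define as a complete stop.

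Omission is temporary: "treatment may resume once the adverse event has resolved as mandated in Table 8.2". When several events occur together, section 8.0 says to "administer dose based on greatest reduction required for any single adverse event observed". A catch-all row for other non-hematologic events at Grade 3 or above requires omission until Grade 2 or below, then restart one level lower. Section 8.41 allows interruption, reduction or discontinuation for liver toxicity according to clinical need and sets no threshold.

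**The concern.** Two patients with identical severe ALT/AST elevation and identical bilirubin at or above 2 x ULN can fall under different mandates. One must stop permanently. The other may be re-exposed after recovery. What separates them is alkaline phosphatase, and the protocol does not explain its role. Section 3.16 sets no entry limit on that marker, and biliary disease may raise it independently of the drug (a clinical assumption). Section 15.17 links raised AST/ALT to liver-cell damage and raised bilirubin to possible liver disease; it says neither of alkaline phosphatase.

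At stake is patient safety, not the two-stage design. Section 8.41 reports three fatal liver-failure cases with ponatinib, one within a week of starting, and says severe liver toxicity was seen in every disease cohort. For other dangerous events Table 8.2 mandates a stop at first occurrence with no added laboratory condition: stroke or myocardial infarction of any grade, thromboembolism from Grade 1, and Grade 4 pancreatitis or left ventricular dysfunction.

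**Working it through.** The plan states no figure to reproduce on this point. The check traces the rules and then sizes the group.

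**1. First-occurrence action when ALT or AST is at Grade 3 or above (Table 8.2)**

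| Bilirubin | Alkaline phosphatase | Row met | Action |
|---|---|---|---|
| ≥ 2 x ULN | > 2 x ULN | Combined and plain | Discontinue |
| ≥ 2 x ULN | ≤ 2 x ULN | Plain only | Omit; may resume at 30 mg |
| < 2 x ULN | > 2 x ULN | Plain only | Omit; may resume at 30 mg |
| < 2 x ULN | ≤ 2 x ULN | Plain only | Omit; may resume at 30 mg |

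Only the first line carries a mandatory permanent stop. The second line is the gap.

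**2. Does other text close the gap?**

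- The section 8.0 rule chooses among rows that are met. In the second line the stop row is not met.
- Bilirubin has no row of its own, so a rise to Grade 3 or above comes under the catch-all row. That row gives omission and a lower dose, not discontinuation.
- Section 8.3 allows a new cycle only if "Any other Ponatinib related adverse event that may have occurred has resolved to" Grade 1 or below, or baseline. This governs recovery, not a permanent stop.
- Under section 8.3, if the drug cannot be restarted within 28 days of the "scheduled Day 1 of a given cycle, the patient will be removed from study treatment". This depends on recovery time, not on how severe the liver tests were.
- Section 16.42 suspends accrual for related Grade 4 or higher non-hematologic events. It does not set an individual patient's dose.

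None of these requires discontinuation at first occurrence.

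**3. Re-exposures the plain row permits before its own mandatory stop**

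45 mg → 30 mg → 15 mg, so 2 re-exposures. For a reduction made at the start of a cycle, the note under the table adds that, after a cycle with no event above Grade 2, "then the dose may be increased, at the investigator's discretion, one level at a time".

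**4. Recovery of bilirubin**

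The plain row names no bilirubin recovery. The section 4.0 chemistry group includes "total bilirubin, creatinine, alkaline phosphatase, SGOT (AST), SGPT (ALT") and, on treatment, is scheduled on Day 1 of each cycle, where section 8.3 applies. It is scheduled at 0 of the 3 mid-cycle visits of Cycle 1 (Days 8, 15 and 22). A mid-cycle restart therefore rests on an unscheduled draw, which section 8.41 foresees. The catch-all row already holds the drug while bilirubin is at Grade 3 or above. What remains is a mid-cycle restart with bilirubin still at Grade 2.

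**5. Size**

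Inputs are the accrual cap of 30 (section 16.22) and the section 15.17 frequencies from prior ponatinib use.

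- Any bilirubin rise, 1% to 10%: 30 x 0.01 = 0.3 and 30 x 0.10 = 3 patients.
- Hepatotoxicity, under 1%: fewer than 30 x 0.01 = 0.3 patients.

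The gap needs bilirubin at or above 2 x ULN together with ALT/AST at Grade 3 or above and alkaline phosphatase at or below 2 x ULN, so on these rates it is a subset of the first group. The rates do not count rises caused by biliary disease.

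**6. Gilbert's threshold used in the fix**

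Entry under the section 3.16 exception means baseline bilirubin above 1.5 x ULN, so 2 x baseline is above 2 x 1.5 = 3.0 x ULN. At assumed baselines of 2.0 and 2.5 x ULN it is 4.0 and 5.0 x ULN.

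**The case against.** The strongest reply is that existing protection is substantial and no danger from the lower alkaline phosphatase pattern is shown. Omission is mandatory, restart is optional and at a lower dose after recovery, removal follows if the 28-day limit is missed, section 8.41 permits stopping at any time, and the safety board reviews the trial at least twice a year. An unexplained threshold is not thereby a wrong one. All of that stands, and it keeps this point at the level of a cheap improvement. It does not supply the missing mandate: the protocol declined to leave the three-marker case to discretion, and nothing in it shows that the two-marker case is safer.

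A reader might infer more than the documents support:

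- *That dosing may simply continue.* It may not; the plain row requires omission.
- *That lower alkaline phosphatase marks the more dangerous pattern, or that the fatal cases showed it.* Section 15.17 does not rank enzyme patterns. Section 8.41 gives no pattern for the deaths, which occurred in blast-phase CML or Ph+ ALL, and it identifies no biliary cohort.
- *That the inequality is a slip and should point the other way.* Nothing in the documents decides this.
- *That bilirubin recovery is uncontrolled.* Section 8.3 and the catch-all row cover most of it.

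**Conclusion.** The concern holds in a limited form. Read as written, Table 8.2 mandates permanent discontinuation at first occurrence for ALT or AST at Grade 3 or above with bilirubin at or above 2 x ULN only when alkaline phosphatase also exceeds 2 x ULN. Otherwise rechallenge at 30 mg and then 15 mg is permitted, and no other rule forbids it. Confidence in this reading of the text is high; the intent behind the condition is unknown.

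The number affected is likely small and may be zero. The accrual cap of 30 is only a logical ceiling and should not be read as an estimate. The estimate assumes that prior ponatinib frequencies carry over; biliary disease could push it up. If that disease often lifts alkaline phosphatase above 2 x ULN, most such patients are already stopped; the documents give no distribution to test this.

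**What to change.** Check the inequality against the source, then replace the combined row with:

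*ALT or AST ≥ Grade 3 AND bilirubin ≥ 2 x ULN: discontinue ponatinib, regardless of alkaline phosphatase (exception: for patients enrolled under the Gilbert's exception in 3.16 whose alkaline phosphatase is ≤ 2 x ULN, use bilirubin ≥ 2 x baseline).*

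Add to the plain ALT/AST row:

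*Any accompanying bilirubin rise must also recover to Grade ≤ 1 or baseline before restart.*

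The new row covers both sides of the 2 x ULN cut, so it works whichever direction was meant. The printed stop for alkaline phosphatase above 2 x ULN is kept for everyone, and the Gilbert's exception applies only where the printed table mandates no stop today. The added sentence tightens the catch-all row, which allows restart at Grade 2.

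The cost is one row with its exception, one sentence and a notice to sites. All four tests are already in the scheduled chemistry group. The downside is a few more permanent stops, some due to biliary disease and not to the drug. Such a stop could occasionally keep a patient from reaching stable disease for 4 or more cycles, which counts toward the primary endpoint (section 16.11) and so toward the 10-patient first stage.

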1.23 Clinical

Iclusig received accelerated approval in the United States (US) (December 2012) and approval in the European Union (EU) (July 2013) for patients with refractory CML or Philadelphia chromosome-positive (Ph+) leukemias. As of 06 January 2014, 753 patients have received ponatinib therapy through clinical studies, and 1312 through global expanded access programs.

Following approval of ponatinib in the US and the EU, more than 900 patients have been treated with ponatinib commercially. Since the previous update to this Investigator Brochure (Version 5, 25 February 2013), regulatory actions were taken by ARIAD Pharmaceuticals (ARIAD) and/or the competent authorities following increased cumulative risk of vascular occlusive events observed in patients using ponatinib. From a development perspective, on 08 October 2013, the US Food and Drug Administration (FDA) placed a partial clinical hold on all new patient enrollments in clinical studies with ponatinib, and a phase 3 study (EPIC: AP24534-12-301) was terminated on 17 October 2013. From a postmarketing authorization perspective, prior approval supplement/type II variation were evaluated by the FDA and the European Medicines Agency (EMA), respectively, to revise ponatinib product information to include updated data and warning/precautions on arterial thromboembolic events, venous thromboembolic events, cardiac failure/left ventricular dysfunction (LVD), and cardiovascular deaths. The type II variation received a positive opinion from Europe's Committee for Human Medicinal Products (CHMP) on 21 November 2013. Subsequent to completion of the Type II variation procedure, a referral procedure under article 20 of regulation (EC) No. 726/2004 was triggered. In the US, while evaluation of new safety data was ongoing, the FDA requested ARIAD on 31 October 2013 to temporarily suspend commercial distribution and marketing of Iclusig in the US. On 20 December 2013, the FDA agreed with the revised US Prescribing Information, and commercialization of Iclusig was resumed in the US in January 2014. Additional information can be found within the Investigator's brochure.

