Clinicians should consider whether the benefits of Iclusig treatment are expected to exceed the risks of therapy. In patients suspected of developing arterial thrombotic events, interrupt or stop Iclusig. A benefit-risk consideration should guide a decision to restart Iclusig therapy. Consider dose modification or discontinuation of Iclusig in patients who develop serious venous thromboembolism and **Monitor for evidence of thromboembolism and vascular occlusion. Interrupt or stop Iclusig immediately for vascular occlusion.**

9.5 **Hypertension**

Treatment-emergent hypertension occurred in 67% of patients (300/449). Eight (2%) treated with Iclusig in clinical trials experienced treatment-emergent symptomatic hypertension as a serious adverse reaction, including hypertensive crisis. Patients may require urgent clinical intervention for hypertension associated with confusion, headache, chest pain, or shortness of breath [*see Adverse Reactions (6)*]. In patients with baseline systolic BP < 140 mm Hg and baseline diastolic BP < 90 mm Hg, 78% (220/282) experienced treatment-emergent hypertension; 49% (139/282) developed Stage 1 hypertension (defined as systolic BP ≥ 140 mm Hg or diastolic BP ≥ 90 mm Hg) while 29% developed Stage 2 hypertension (defined as systolic BP ≥ 160 mm Hg or diastolic BP ≥ 100 mm Hg). In 131 patients with Stage 1 hypertension at baseline, 61% (80/131) developed Stage 2 hypertension. Monitor and manage blood pressure elevations during Iclusig use and treat hypertension to normalize blood pressure. Interrupt, dose reduce, or stop Iclusig if hypertension is not medically controlled.

9.6 **Heart Failure**

Fatal and serious heart failure or left ventricular dysfunction occurred in 5% of Iclusig-treated patients (N = 22). Eight percent of patients (N = 35) experienced any grade of heart failure or left ventricular dysfunction. Monitor patients for signs or symptoms consistent with heart failure and treat as clinically indicated, including interruption of Iclusig. Consider discontinuation of Iclusig in patients who develop serious heart failure

- 9.7 **Diarrhea:** This could be managed conservatively with loperamide. The recommended dose of loperamide is 4 mg at first onset, followed by 2 mg every 2-4 hours until diarrhea free (maximum 16 mg/day).

In the event of Grade 3 or 4 diarrhea, the following supportive measures are allowed: hydration, octreotide, and antidiarrheals.

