If diarrhea is severe (requiring intravenous rehydration) and/or associated with fever or severe neutropenia (grade 3 or 4), broad-spectrum antibiotics must be prescribed. Patients with severe diarrhea or any diarrhea associated with severe nausea or vomiting **should be hospitalized** for intravenous hydration and correction of electrolyte imbalances.

- 9.8 **TLS:** Clinically significant Tumor Lysis Syndrome (TLS) has been reported at the initiation of treatment with TKIs in CML patients. The patients at risk of TLS are those with high tumor/leukemic burden prior to treatment. These patients should be monitored closely, especially at the initiation of treatment. Appropriate TLS precautions and prophylactic treatment (such as aggressive hydration with fluids and the initiation of allopurinol 600 mg/day or other appropriate treatments) should be initiated prior to the start of therapy for those at risk for TLS. Rasburicase and other appropriate treatments for hyperuricemia or TLS are permitted.

- 9.9a **Prolonged QTcF:** If a prolongation of QTcF is observed, it is important to perform serum electrolyte analysis (including potassium, calcium, and magnesium) and correct any significant abnormalities with supplements if below normal limits. It is also necessary to review all concomitant medications the patient is on and discontinue medications that are known or suspected to cause QT prolongation.

If no contributing reason is identified and the reason for QTcF prolongation is believed to be due to study medication, dose interruption and reduction guidelines for general non-hematologic toxicities in 8.2 for ponatinib should be followed. Additionally, weekly ECG monitoring is recommended for 4 weeks upon resumption of study drug, then monthly for 6 months, and then every 3 months for the remainder of the study, or more frequently as clinically indicated.

- 9.9b Based on *in vitro* studies, ponatinib is a substrate of CYP3A4/5 and to a lesser extent CYP2C8 and CYP2D6. Ponatinib also inhibits the P-glycoprotein (P-gp), ATP-binding cassette G2 (ABCG2) [also known as BCRP], and bile salt export pump (BSEP) transporter systems *in vitro*.

Drugs That Are Strong Inhibitors of CYP3A Enzymes

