10.0 Adverse Event (AE) Reporting and Monitoring

10.1 Adverse Event Characteristics

CTCAE term (AE description) and grade: The descriptions and grading scales found in the revised NCI Common Terminology Criteria for Adverse Events (CTCAE) version 4.0 will be utilized for AE reporting. All appropriate treatment areas should have access to a copy of the CTCAE version 4.0. A copy of the CTCAE version 4.0 can be downloaded from the CTEP web [site](http://ctep.cancer.gov/protocolDevelopment/electronic_applications/ctc.htm): (http://ctep.cancer.gov/protocolDevelopment/electronic_applications/ctc.htm)

10.11 Adverse event monitoring and reporting is a routine part of every clinical trial. First, identify and grade the severity of the event using the CTCAE version 4.0. Next, determine whether the event is expected or unexpected (see Section 10.2) and if the adverse event is related to the medical treatment or procedure (see Section 10.5). With this information, determine whether the event must be reported as an expedited report (see Section 10.). Expedited reports are to be completed within the timeframes and via the mechanisms specified in Sections 10.4. All AEs reported via expedited mechanisms must also be reported via the routine data reporting mechanisms defined by the protocol (see Sections 10.6 and 18.0).

- 10.12 Each CTCAE term in the current version is a unique representation of a specific event used for medical documentation and scientific analysis and is a single MedDRA Lowest Level Term (LLT). Grade is an essential element of the Guidelines and, in general, relates to **severity** for the purposes of regulatory reporting to NCI.

NOTE: A severe AE, as defined by the above grading scale, is **NOT** the same as serious AE which is defined in the table in Section 10.4.

- 10.13 Medical conditions/diseases present before starting study treatment are only considered adverse events if they worsen after starting study treatment (any procedures specified in the protocol). Adverse events occurring before starting study treatment but after signing the informed consent form are recorded. Abnormal laboratory values or test results constitute adverse events only if they induce clinical signs or symptoms or require therapy, and are recorded.

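### Table 8.2 requires ponatinib to stop for Grade 4 left ventricular systolic dysfunction and for its recurrence at 15 mg, but requires neither for heart failure recorded without it

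*Combined protocol and SAP*

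**What the plan says.** **Named cardiac rows (Table 8.2).** The Cardiac Disorders block names LVSD and myocardial infarction only. LVSD of Grade 3 or higher is omitted and resumed at 45 mg, then 30 mg, then 15 mg on successive recurrences, each time after recovery to Grade 1 or less. Recurrence at 15 mg means discontinuation. The next row, "Left ventricular systolic dysfunction ≥ Grade 4", means discontinuation outright, as does myocardial infarction of any grade.

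**Catch-all row (Table 8.2).** For other non-hematologic events of Grade 3 or higher the action is: "Omit drug and follow patient at least weekly until adverse event has resolved to grade ≤ 2, restart agent at next lower dose level". The row adds: "See sections 8.41 through 8.47 for guidance on other non-hematologic events". A note below the table says that reductions "beyond the two dose-reduction steps (levels -1 and -2) will be at the discretion of the treating physician", if the patient is kept on study.

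**Heart failure (section 9.6).** It reports heart failure and left ventricular dysfunction together, asks for monitoring and treatment including interruption, and ends: "Consider discontinuation of Iclusig in patients who develop serious heart failure". Section 1.23 also names the two conditions as a pair in the revised product warnings.

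**Term-based recording (section 10.12).** "Each CTCAE term in the current version is a unique representation of a specific event".

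**The concern.** Table 8.2 is organised by CTCAE term, so the term written on the form selects the row. Two conditions that the protocol treats as a pair then carry different obligations. Recorded as LVSD, a Grade 4 event ends treatment. Recorded only as heart failure, a Grade 4 event may be followed by a restart at 30 mg once it has improved to Grade 2, and a recurrence at 15 mg brings no required stop. The drug has caused fatal heart failure or left ventricular dysfunction in earlier trials (section 9.6). At stake is the safety of an individual patient and consistent handling between investigators. The efficacy analysis is not involved.

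**Working it through.** No figure in the plan needs reproducing. The check is a comparison of the rules.

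**1. Which row applies.** Heart failure appears in no row of Table 8.2. At Grade 3 or higher it is a non-hematologic event without its own row, so the catch-all applies. Section 9.9a handles an unlisted event in the same way. For QTcF prolongation attributed to study drug, it says that the "dose interruption and reduction guidelines for general non-hematologic toxicities in 8.2 for ponatinib should be followed".

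**2. The two routes side by side.**

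| Situation | Recorded as LVSD | Recorded only as heart failure |
|---|---|---|
| First Grade 3 event at 45 mg | May resume at 45 mg | May restart at 30 mg |
| Recovery needed | Grade 1 or less | Grade 2 or less |
| Grade 4 | Discontinue | May restart one level lower |
| Recurrence at 15 mg | Discontinue | Treating physician's discretion |
| Mandatory stops | 2 | 0 |

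The first line runs the other way: for a first Grade 3 event the catch-all is stricter on dose. The gap lies in the Grade 4 and 15 mg lines.

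**3. Does the catch-all's pointer fill the gap?** Sections 8.41 to 8.47 cover, in order, liver, pancreas, neuropathy, eye, fluid retention, arrhythmia, and wound healing with perforation. None of the seven sets a rule for heart failure. The section that does, 9.6, is not in the pointer and does not refer to Table 8.2.

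**4. Do other rules impose the stop?**
- Section 8.0 applies the greatest reduction among recorded events. This brings in the LVSD rows only if LVSD is also recorded.
- Section 4.0, footnote 10, schedules echocardiograms every 2 cycles. This makes a record of LVSD more likely but does not guarantee one.
- Section 8.3 requires ponatinib-related events to return to Grade 1 or baseline before a new cycle. The definition of Omit allows resumption within a cycle (its example is omission on Day 8 and resumption on Day 15), where the catch-all's Grade 2 threshold governs.
- Section 8.3 also ends study treatment if drug cannot be restarted within 28 days of the scheduled Day 1. That does not stop a patient who recovers in time.
- Section 16.42 counts related Grade 4 or higher non-hematologic events towards suspending accrual. It does not govern the affected patient's dosing.

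None of these is a mandatory stop for Grade 4 heart failure or for its recurrence at 15 mg.

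**The case against.** The strongest case against is that heart failure already has its own guidance and that whether to mandate discontinuation is a design choice. Section 9.6 asks the investigator to consider stopping for serious heart failure. A life-threatening event, or one needing at least 24 hours in hospital, is serious under section 10.4, so 9.6 reaches the events of concern. This stands as a real safeguard, but considering a stop is weaker than the required stop for the paired condition.

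A reader might infer several stronger points that the documents do not support:

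- **That the protocol directs a restart after Grade 4 heart failure.** The row's wording alone suggests it, but the definition of Omit under the table says treatment may resume. The row permits a restart and sets its terms.
- **That Grade 4 means the same for both terms.** The CTCAE list is linked and not reproduced, so equivalence of grades is not shown. That heart failure can be recorded separately is inferred from sections 10.12 and 9.6.
- **That Table 8.2 stops drug for every other Grade 4 event.** It does not: Grade 4 hypertension, and Grade 4 amylase elevation, may resume at 30 mg.
- **That the missing stop at 15 mg is peculiar to heart failure.** It applies to every catch-all event, so counting the named rows that have such a stop proves nothing specific to heart failure. What singles heart failure out is the protocol's own pairing of it with LVSD.
- **That the number of affected patients can be estimated.** Applying section 9.6's 5% to the maximum of 30 patients gives 30 × 0.05 = 1.5 serious events. But the 5% (22 patients) and 8% (35 patients) combine both conditions and come from earlier trials, and section 3.29h excludes recent heart failure and an ejection fraction of 50% or less.

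**Conclusion.** The inconsistency is real and minor. Table 8.2 imposes two mandatory stops for LVSD and none for heart failure recorded without it, and section 9.6 narrows that difference without closing it.

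The conclusion rests on three assumptions: that an event can be recorded as heart failure without LVSD; that the catch-all governs events with no row, as section 9.9a illustrates; and that the explicit stop at 15 mg in the LVSD row prevails over the general note on reductions beyond level -2.

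The situation it affects is narrow: for the Grade 4 gap, no LVSD on record, recovery in time to restart, and an investigator who resumes despite section 9.6. Its frequency here cannot be derived, and the primary endpoint and two-stage design are unaffected.

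**What to change.** Add two lines to the Cardiac Disorders block of Table 8.2:
- Heart failure, Grade 4: discontinue ponatinib.
- Heart failure, Grade 3 or higher, recurring at 15 mg: discontinue ponatinib.

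Cross-refer section 9.6 to these lines, as section 9.9a already refers to section 8.2. Leave the LVSD rows and the existing catch-all dose rule for Grade 3 heart failure unchanged. A new Grade 3 step-down for heart failure is not needed: the catch-all already restarts one level lower, whereas the LVSD row allows a return to 45 mg, and which is preferable is open to debate.

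The cost is a wording amendment, with no added procedures or patients. The downside is that a few patients may stop ponatinib who could otherwise have restarted it.
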